### **Overall Project Statistical Plan:**

SA1: Changes in hepatic fat will be compared to changes in insulin resistance, beta cell function and 31P-MRS and metabolomics score. Results will be adjusted for absolute and percent weight loss.

SA3: Pearson correlations between 31P-MRS rate of ATP recovery, metabolomics outcomes, hepatic fat fraction, MRE, Oroboros outcomes and biopsy scores will be performed to see which

minimally invasive measures relate most to biopsy markers. Liver measures will also be compared to insulin sensitivity and insulin secretion from the MMT.

Overall Power analysis:

SA1: The data collected for SA3 is to be preliminary data to provide background data for future additional studies in youth.

SA2/SA3: Relation of metabolic outcomes for this type of protocol typically requires 6-8 participants, especially with such a homogenous participant group. However, as it is known that African American tend to have different hepatic fat metabolism patterns compared to Hispanics, we have allowed for 10 participants.

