### I. Hypotheses and Specific Aims:

NAFLD has become a major public health problem in the United States because of its high prevalence, association with serious cardiometabolic complications and progression to cirrhosis and liver failure. NALFD is characterized by increased intrahepatic triglyceride content (>5.5% of the liver volume or more than 5% of hepatocytes contain triglyceride), and progression to inflammation and fibrosis. NAFLD is associated with increased risk of developing type 2 diabetes (T2D), hypertension, and coronary heart disease. Obesity is an important risk factor for NAFLD; NAFLD occurs in ~70% of adults with obesity and in ~35% of children with obesity.

However, data from several studies suggest the histological manifestations and progression to fibrosis are different in adults and children with NAFLD. Differences between the ages suggest distinct pathology as i) Youth with NAFLD may progress to liver failure fairly rapidly, by early adolescence, as compared to a more indolent course in adults and ii) biopsy criteria are distinct with periportal steatosis and fibrosis in youth and sinusoidal ballooning and fibrosis in adults. Alterations in mitochondria function, secondary to an influx of substrates from the diet and dysfunction muscle and adipose tissue are thought to contribute to NAFLD. We hypothesize that alterations in mitochondrial energy and substrate metabolism are involved in the pathogenesis and pathophysiology of NAFLD and these factors differ in children and adults. A better understanding of intrahepatic regulation of energy and intermediary metabolism in children and adults with NAFLD is needed to provide a framework for future studies designed to prevent and treat NAFLD across the lifespan.

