## **HYPOTHESIS:**

- 1) NAFLD status will be improved by 1-year post-bariatric surgery and this may relate to post-prandial glucose and FFA concentrations and hepatic mitochondrial metabolism.

- 2)  $^{31}\text{P}$ -MRS, blood and liver isotopomer analysis and metabolomics can be used as surrogate measures to assess hepatic function in NAFLD

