**Aim 3:** Determine hepatic mitochondrial activity in vivo using  $^{31}\text{P}$ -MRS, isotopomer and plasma metabolomic analysis and ex vivo using Orobos in youth with severe obesity. NAFLD features will be further characterized using liver histology to assess steatosis and NASH and by using MR elastography to assess global hepatic fibrosis. Alterations in glucose and fat metabolism will be assessed with a mixed meal tolerance test (MMT). Comparisons between these surrogate markers and biopsy samples will help identify minimally invasive measures to predict NAFLD severity without the need for future biopsies.

**Hypothesis:** We hypothesize that alterations in mitochondrial energy and substrate metabolism are involved in the pathogenesis and pathophysiology of NAFLD. A better understanding of intrahepatic regulation of energy and intermediary metabolism in children with NAFLD is needed to provide a framework and identify minimally invasive biomarkers for future studies designed to prevent and treat NAFLD.

**Rationale:** NAFLD is unfortunately an increasing common complication of pediatric obesity. Youth onset metabolic disease confers an early and more severe morbidity and earlier mortality than adult onset disease, emphasizing the urgency of treating this population.

**Methods:** We will compare multiple methods of non-invasive and minimally invasive measure of hepatic metabolism with the gold standard but invasive liver biopsy.  $^{31}\text{P}$ -MRS and isotopomer analysis will be used to assess hepatic oxidative phosphorylation, MRI for hepatic fat fraction

and MR elastography for liver stiffness. Serum for metabolomics analysis will be collected and metabolites which related to MR and biopsy measure identified (targeted analysis for fatty acids, acycarnitines and bile acids). Ex vivo measures of mitochondrial function will be measured in liver biopsy samples (already being collected during bariatric surgery for clinical NALFD staging) with oroboros technologies. NAFLD staging data from the pathology lab will also be collected. Alterations in glucose and fat metabolism will be assessed with a mixed meal tolerance test (MMT).

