## **VIII. Summarize Knowledge to be Gained:**

**Overall Expected Results:** We anticipate that we will identify several minimally invasive biomarkers in severely obese patients that can be used to predict NAFLD status. We also anticipate that we will generate preliminary data as to the relationship between type 2 diabetes risk and liver health in these patients, and how these both change following bariatric surgery. This data would then provide the background evidence for additional post-bariatric mechanistic studies and future therapeutic trials.

**Significance:** Recent evidence in adults with severe obesity indicates that 60-70% have NAFLD. And youth may have a similar prevalence. NAFLD has been described as the primary driver of worsening metabolic syndrome and CVD in obesity across populations, and can progress to cirrhosis and liver failure. Thus, understanding the relative contributions of NAFLD to metabolic disease critical to designing strategies to improve the long-term health of these youth and reduce their risk of T2D, CVD and liver failure. Further as bariatric surgery is now being advocated for treatment of NAFLD, T2D and severe obesity, understanding the effects and mechanism on metabolic disease are critical.

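### SA3 plans only correlations with biopsy scores, which give no classification or prediction error, while the protocol expects markers that predict NAFLD status

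*Combined protocol and SAP*

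**What the plan says.** The SA3 paragraph of the Overall Project Statistical Plan (section VII) states the method in one sentence: "Pearson correlations between 31P-MRS rate of ATP recovery, metabolomics outcomes, hepatic fat fraction, MRE, Oroboros outcomes and biopsy scores will be performed". Its purpose is to see which "minimally invasive measures relate most to biopsy markers". The only other SA3 analysis is "Liver measures will also be compared to insulin sensitivity and insulin secretion from the MMT", which does not involve biopsy. No cut-off, sensitivity, specificity, ROC curve, agreement analysis, prediction model or validation step is described.

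Three other places set expectations for the same data:

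- Aim 3 in Specific Aims says the comparisons will "help identify minimally invasive measures to predict NAFLD severity without the need for future biopsies".
- Section VIII, under the expected results, anticipates that "we will identify several minimally invasive biomarkers in severely obese patients that can be used to predict NAFLD status".
- The second hypothesis includes the statement that "metabolomics can be used as surrogate measures to assess hepatic function in NAFLD".

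Section I defines NAFLD by increased intrahepatic triglyceride, given as ">5.5% of the liver volume or more than 5% of hepatocytes contain triglyceride". The statistical plan does not use either limit.

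The Overall Power analysis calls the SA3 data preliminary, for use in later studies (the sentence is printed under the SA1 label). Section IV calls the study a pilot.

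**The concern.** NAFLD status is a classification, and predicting it means assigning participants to one side of a limit with a known error rate. A correlation coefficient does not depend on the scale, offset or cut-off of the marker. A marker can correlate strongly with biopsy grade and still misclassify many participants, or read systematically high or low at the limit that defines disease. Changing to a rank coefficient does not alter this.

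The 1-year visit repeats the baseline procedures without a biopsy, so surgery is the only point at which the non-biopsy measures can be checked against histology. If only correlations are reported there, a modest r could be read as evidence that a marker is ready to predict status. Nothing in the planned output would show the error that comes with it.

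**Working it through.** **Is there a figure to reproduce?** The plan gives no accuracy target. Its one SA2/SA3 figure is 10 participants (6-8 said to be typical), with no significance level, power or target correlation, so it cannot be reproduced. The Description of Population text aims for 16. Results below are for n=10 and n=16.

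**Step 1: smallest significant correlation** (assumed: two-sided 5% test). r = t / sqrt(n - 2 + t²), where t is the 97.5% point on n - 2 degrees of freedom.

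- n=10: 2.306 / sqrt(8 + 5.318) = 0.632
- n=16: 2.145 / sqrt(14 + 4.600) = 0.497

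**Step 2: misclassification implied by r** (assumed: bivariate normality, marker and biopsy score each split at the median). Proportion misclassified = 0.5 - arcsin(r)/π.

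| r | misclassified |
|---|---|
| 0.497 | 33% |
| 0.632 | 28% |
| 0.80 | 20% |

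As a cross-check, a bivariate-normal simulation with biopsy dichotomised at 50-60% prevalence gives, for r=0.632, an AUC of about 0.80 and best sensitivity and specificity of about 72% each.

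**Step 3: correlation is not agreement.** Suppose a marker equals 0.5 × reference + 5, with the reference uniform from 2 to 30 (assumed). Then r = 1.00. At a cut of 5.5 the marker is positive whenever the reference exceeds 1, which is everyone. Those with a reference between 2 and 5.5 are wrongly called positive: 3.5/28 = 12.5%. This matters only for a measure on the same scale as the reference.

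**Step 4: precision of the correlation.** With Fisher z, an observed r of 0.70 has a 95% CI of 0.13 to 0.92 at n=10 and 0.31 to 0.89 at n=16.

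**Step 5: precision of an accuracy analysis.** When all k of k are classified correctly, the exact lower 95% limit is 0.025^(1/k). The protocol puts NAFLD above 50% in young bariatric candidates and at 60-70% in adults with severe obesity, so I take 50-70%.

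- n=10, 50%: 5 cases. 5/5 detected gives a lower limit of 48%.
- n=10, 70%: 3 non-cases. 3/3 correct gives a lower limit of 29%.
- n=16, 50%: 8 cases. 8/8 detected gives a lower limit of 63%.

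**Step 6: which AUC to report.** I simulated one normal marker with a linear discriminant, equal numbers of cases and non-cases, 4,000 runs.

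| n | true AUC | mean leave-one-out AUC | mean plain AUC |
|---|---|---|---|
| 10 | 0.50 | 0.24 | 0.50 |
| 10 | 0.80 | 0.58 | 0.80 |
| 16 | 0.50 | 0.26 | 0.50 |
| 16 | 0.80 | 0.68 | 0.80 |

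Leave-one-out AUC is strongly biased downward at these sizes. The plain rank-based AUC is not, and for a single marker with its direction fixed in advance it needs no fitted model.

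**The case against.** The strongest reply is that SA3's statistical question is which measures relate most closely to biopsy, and correlation answers that question. The study calls itself a pilot, the SA3 data are called preliminary, and the biopsy and MR measures are secondary or exploratory. Aim 3 says only that the comparisons will help identify measures. At this size an accuracy analysis cannot establish a biomarker either.

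Much of this stands. A reader might infer that the protocol promises a validated substitute for biopsy. It does not: the Aim 3 wording is softer, and section VIII states an anticipated result. A reader might also infer that the protocol sets 5.5% as its MR limit. Section I does not mention MR, and the imaging section gives no cut-off for the Dixon fat fraction.

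The figures are also only illustrative. A median split is not the NAFLD limit, biopsy scores are unlikely to be normal, and under those assumptions r does carry information about error. Agreement on scale is irrelevant for spectroscopy and metabolomics, which do not share the biopsy scale.

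The mismatch itself is not answered. The underpowering caveat in section IV concerns associations between changes in metabolism and NAFLD status. In section VIII, the reference to preliminary data is attached to diabetes risk and liver health, not to the biomarker sentence. More participants would narrow the interval around r but would still yield no classification error.

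**Conclusion.** The point holds as a mismatch between the planned analysis and the expected conclusion in a pilot. SA3 as written can rank markers by association. It cannot show that any marker predicts NAFLD status, because no classification or prediction error is planned.

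For scale, markers that just reach significance would misclassify about 28% (n=10) to 33% (n=16) of participants, and r=0.80 about 20%. These figures assume bivariate normality and a median split; the first two also assume a two-sided 5% test. They show that a significant correlation can go with substantial error, and are not forecasts for this study. The conclusion about the type of analysis does not depend on them.

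This is an inexpensive improvement to a secondary and exploratory part of the study. It does not affect the primary outcome.

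**What to change.** Add the following to SA3, labelled exploratory:

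1. For each pre-listed marker, with its direction fixed in advance, report the plain empirical (rank-based) AUC for biopsy-defined NAFLD with a 95% CI, alongside the correlation with its 95% CI. Use the section I histological limit of more than 5% of hepatocytes. Do not use leave-one-out AUC. State the numbers of cases and non-cases; if one group is empty, the AUC cannot be estimated and the plan should say so.
2. Cross-tabulate MR fat fraction against biopsy steatosis and report sensitivity and specificity with exact 95% CIs. Use the 5.5% limit only if the sponsor confirms and prespecifies that it applies to its Dixon fat fraction.
3. Restate the expected result in section VIII as candidate markers for validation in a larger cohort.

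The cost is SAP wording and a few tables from data already collected, with no new visit, sample or participant. The downside is that the intervals will be wide even for an error-free marker, as shown above, and the stated conclusion becomes less favourable. Items 1 and 2 will not establish a biomarker at this size; they make the uncertainty visible. Item 3 alone would remove the mismatch.

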## **VIII. Summarize Knowledge to be Gained:**

**Overall Expected Results:** We anticipate that we will identify several minimally invasive biomarkers in severely obese patients that can be used to predict NAFLD status. We also anticipate that we will generate preliminary data as to the relationship between type 2 diabetes risk and liver health in these patients, and how these both change following bariatric surgery. This data would then provide the background evidence for additional post-bariatric mechanistic studies and future therapeutic trials.

**Significance:** Recent evidence in adults with severe obesity indicates that 60-70% have NAFLD. And youth may have a similar prevalence. NAFLD has been described as the primary driver of worsening metabolic syndrome and CVD in obesity across populations, and can progress to cirrhosis and liver failure. Thus, understanding the relative contributions of NAFLD to metabolic disease critical to designing strategies to improve the long-term health of these youth and reduce their risk of T2D, CVD and liver failure. Further as bariatric surgery is now being advocated for treatment of NAFLD, T2D and severe obesity, understanding the effects and mechanism on metabolic disease are critical.

